In that context, a $[^{11}\text{C}]\text{raclopride}$ PET study showed a robust release of dopamine following an alcohol challenge compared to placebo in social drinkers who carried the G allele (Ramchandani et al. 2011). The effect of the G allele on μ opioid receptor binding with PET and $[^{11}\text{C}]\text{carfentanil}$ has been studied in alcohol-dependent participants and in smokers (Weerts et al. 2012; Ray et al. 2011). There was no effect of alcohol dependence on the binding of $[^{11}\text{C}]\text{carfentanil}$, but carriers of the G allele had lower global binding potential (BP_{ND}) for the radioligand (Weerts et al. 2012). A similar lower binding potential was observed in smokers carrying the G allele, and the lower binding potential in some of the regions assayed was associated with greater subjective reward from smoking (Ray et al. 2011).

The effect of the G allele on pain perception has been studied in various conditions. Fillingim et al. (2005) demonstrated a significant difference in pressure pain threshold in individuals with the 118G variant SNP. Interestingly, this threshold difference was higher among men and lower among women with the 118G SNP as compared to controls. Nonetheless, the effect of fentanyl on perceived labor pain was greater in women carrying the G allele than in women homozygous for A resulting in the need for less analgesic (Landau et al. 2008). However the effect was opposite in a study by Oertel et al. (2008).

Bond et al. (1998) using *Xenopus* oocyte cells, found that receptors encoded by the variant 118G allele showed increased affinity for the endogenous μ -opioid ligand β -endorphin *in vitro*, leading to increased activation of G-protein activated inwardly rectifying potassium channels following binding of β -endorphin (Bond et al. 1998). However, Befort et al. (2001) found no difference in binding affinity of β -endorphin between wild type and A118G-coded μ -opioid receptors using an *in vitro* model with COS cells. Similarly, Beyer et al. (2001) found no difference in μ -opioid binding between wild type and A118G coded receptors using an *in vitro* HEK 293 cell model. These discrepant *in vitro* results reinforce the importance of examining the functional role of the μ -opioid receptor in the correct context, both at the cellular level, where coupling, etc. may be determined by cell type, and at the level of the integrated organism.

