Participants will be given a meal once collection of dependent measures is complete. After the meal, orthostatic vitals will be obtained and if there is no evidence of symptomatic orthostasis the participant will be discharged.

Visit 2 Morphine injection with subjective and physiological measures (Toleration Study):

The purpose of this visit is two-fold. The first is to reduce the likelihood that side effects like vomiting will occur in the PET scanner. The second is to obtain data on the participant's responses (pain response and pupil response) to morphine at a time when the participant is not in the scanner when such measurements would be more difficult to acquire. Following a prestudy nursing assessment, which includes urine toxicology, breathalyzer, CO monitoring, HR, BP, RR, and weight, two indwelling intravenous catheters will be inserted, one each into the antecubital vein of the arm using sterile technique. The following table summarizes the prestudy nursing assessments obtained:

Measurement	Parameter(s) to proceed
Breathalyzer	Negative
CO test	≤ 15 ppm
Urine toxicology	Negative
Heart rate*	≥50 bpm and ≤105 bpm
Systolic blood pressure*	≥95 mmHg and ≤135 mmHg
Diastolic blood pressure*	≥60 mmHg and ≤90 mmHg
Respiratory rate*	≥8 and ≤24 breaths per minute
Oxygen saturation*	≥94%

One catheter will be used for the placebo and morphine injections and the other will be used for blood sampling. A nurse will monitor HR, BP, RR, ECG and blood oxygen saturation throughout the study. Measurements will be recorded at 5 min intervals after either the placebo or morphine injection. The measurements will be recorded for at least

60 min or until values have returned to the normal range. A nurse will place the AutoSense ECG electrodes and respiration band on the participant's chest for continuous physiological monitoring throughout the session. Monitoring by the AutoSense will be in addition to monitoring by traditional methods.

Baseline measurements (as described below) will then be obtained. After this, the placebo injection (normal saline in a volume equal to that used for the morphine injection) will be given (at approximately 9:45AM).

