At baseline as well as during and after the injection, the following measures will be obtained, following the schedule outlined in the study-session flow-sheet (Table 1): Subjective questionnaires: a visual analog scale of high and intoxication See Appendix I. for Drug Effects Questionnaire (DEQ) (Holdstock and de Wit 1999). The DEQ consists of four visual analog scales used to describe current drug effects (feel drug effects, none (0) to a lot (100)]; like the effects they feel, dislike (0) to neutral (50) to like extremely (100); feel high, not at all (0) to a lot (100); and (4) would like more not at all (0) to a lot (100).

Objective Measurements: 1) Pupil constriction(Grace et al. 2010), cold pressor test (Posner 1991), and 2) Blood will be drawn at baseline and at 10 min after the injection for analysis of blood chemistries potentially responsive to an opiate challenge (including, but not limited to ACTH and cortisol) (Jaffe 1985).

Cold Pressor Test: The cold water pressor test evaluates discomfort or pain when the nondominant hand is first placed in a warm water bath (37° C) for 2 min, then transferred to an ice water bath (0° C). The participant is instructed to immerse his/her hand in the ice water for up to 3 min, but could withdraw the hand at any time if the pain becomes too great. Participants are instructed to report verbally when they first sensed pain. This time measures pain threshold. Time to withdrawal measures pain endurance (Posner 1991). See scoring sheet in Appendix I.

Pupil constriction test: Participants will be instructed to sit quietly, blinking as little as possible while the pupillograph is positioned over the right eye by the operator. While the participant focuses on a fixed point. The resting pupil diameter will be measured for 2 s every 20 s for a total of one minute. This test is a modification of a previously reported method (Grace et al. 2010) to remain within the time of the expected drug effect and will commence four minutes after the participant puts his hand in the cold water.

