The participant will be returned to the lounge for a relaxation period and a snack or lunch. In early afternoon, the participant will return to the study room for the morphine injection, which will be administered by an NIH Credentialed physician with ACLS certification. Participants will receive an injection of 10 mg/70 kg morphine (2 mg/ml) administered by an NIH Credentialed physician over 1 minute. The tests described above will be repeated. The participant will be monitored by an NIH Credentialed physician for the next 60 min or until HR, RR, BP, EKG and oxygen saturation have returned to normal ranges. Values will be recorded approximately every 5 min (+/- 1) for the next 60 min after the injection or until they have returned to normal ranges.

Table for Visit 2

Minutes	BL	0	5	10	15	20	25	30	35	40	45	50	55	60 (plus additional records q. 10 min if not within normal range)
Morphine or placebo administration		x												
HR, BP, RR, O2 Sat, EKG recorded *	x		x	x	x	x	x	x	x	x	x	x	x	x
Cold Pressor Test			x											
DEQ	x			x		x		x		x		x		x
Pupil constriction	x			x		x		x						
Blood draw for ACTH/cortisol* *	x		x				x							
VAS														x

Please note the timing for these parameters will be as close as possible to the stated times, but may not be at exactly these times. Data from cold pressor test, DEQ and pupillary constriction will be collected in sequence, not at the same time.

*Please note monitoring of these parameters will be continuous until they have returned to normal ranges and recording of these parameters will continue at 10 min intervals if they have not returned to normal ranges. It is expected that following the placebo injection, these values will be normal throughout the study, but they will be monitored for at least 60 min.

** First blood draw for ACTH/cortisol will be after cold pressor test and DEQ, but before pupil constriction test.

The AutoSense electrodes and respiration belt will be removed at the end of the session.

Visits 3 and 4: PET studies of [¹¹C]raclopride binding with and without morphine:

Participant will be brought to the Clinical Center via taxi during the afternoon or early evening of each day before the scheduled PET studies.

Outline of PET session procedures:

- 1) Two IV lines will be started, one for injection of [¹¹C]raclopride, the other for the morphine or placebo (normal saline in a volume equal to that used for the morphine injection) injection.

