To evaluate for the possibility of adverse events, a safety assessment evaluation will be conducted at the completion of the last of the PET scan / injection study sessions. This assessment will include vital sign determination, EKG, CBC, and blood chemistry. The Lead Investigator or her designate will contact the participant by phone, approximately one week after the completion of the study to evaluate for the possibility of any unexpected adverse events.

Participants will be withdrawn from the study if they do not follow the instructions outlined in the protocol and informed consent form. Participants will also be withdrawn if they cannot tolerate the morphine injection and demonstrate any signs of untoward effects. Participants may also, at any time, choose to discontinue their participation in the study.

9. Outcome measures

- a. The two primary outcome measures are:
 - 1) $[^{11}\text{C}]\text{raclopride}$ binding potential in striatal areas of the brain
 - 2) Subjective perceptions of morphine intoxication and opiate effects.
- b. Secondary measures are:

- 1) levels of neuroendocrine measures (ACTH, cortisol)
- 2) pupillary constriction, respiratory rate, pain response

10. Statistical Analysis

a. Analysis of data/ study outcomes

For the primary analyses, dependent variables (subjective and objective responses in the laboratory, post-morphine injection raclopride binding potential) will be analyzed using analysis of variance, with genotype as the independent factor. The role of drug and alcohol drinking history and family history of drug abuse/alcoholism as well as self-reports of ancestry and genetically derived ancestry scores will be evaluated as covariates in the analysis. The level of significance will be set at 0.05.

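### The text implies a pre-injection cold pressor test that the Visit 2 table does not schedule, and Section 10a does not bring the same-day post-placebo immersion into the pain analysis

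*Combined protocol and SAP*

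**What the plan says.** **Timing of the test.** The opening summary (Design) speaks of measures before and after injection and includes the cold-water pain rating among them. Section 4d, Visit 2, places a baseline set ahead of the placebo injection: "Baseline measurements (as described below) will then be obtained". It then introduces the list of measures with "At baseline as well as during and after the injection, the following measures will be obtained", subject to the schedule in a flow-sheet. The list includes the "cold pressor test (Posner 1991)".

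The Table for Visit 2 applies to "Morphine or placebo administration". Its baseline column is marked for vital signs, DEQ, pupil constriction and the ACTH/cortisol draw. The row "Cold Pressor Test" has a single mark, at 5 minutes. A footnote puts the first ACTH/cortisol draw after the cold pressor test.

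**Order of injections.** Section 4d gives placebo first and morphine second on the same day, and after morphine "The tests described above will be repeated". Section 4a likewise describes measures after placebo and after morphine.

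**Analysis.** Section 10a takes as outcomes the "dependent variables (subjective and objective responses in the laboratory, post-morphine injection raclopride binding potential)" and analyses them by analysis of variance on genotype. The candidate covariates are drug and alcohol history, family history and ancestry. Section 9b lists pain response as a secondary measure.

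**Background.** After citing a pressure-pain study, Section 1 states that "this threshold difference was higher among men and lower among women with the 118G SNP as compared to controls".

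**The concern.** There are two linked gaps. First, staff could read the visit instructions in different ways and give different numbers of ice-water immersions. Men would then reach the post-morphine test with different prior exposure to the stimulus.

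Second, the primary objective in Section 2 is the role of genotype in the effects of morphine. For pain, an effect of morphine is a change from a drug-free state in the same man. Section 10a names no such reference for the pain measure. The genotype groups are not formed by randomisation, so nothing in the design equalises their basal pain sensitivity, and the protocol itself cites evidence of a pain-threshold difference with 118G in men. If post-morphine times were compared as they stand, a difference between groups could be reported as differential analgesia when the groups differed before any drug was given.

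**Working it through.** **Step 1: how many immersions per man?**
- By the table: one after placebo and one after morphine, so two.
- By the text, with a baseline set before placebo only: three.
- By the text, if the whole sequence including a baseline is repeated around the morphine injection: four. This is an inference; no passage states a second pre-injection immersion.
- The blood-draw footnote does not settle it. If its first draw is the one in the baseline column, a baseline immersion is implied. If it is the first draw after injection, none is.

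**Step 2: is there a drug-free reference?** Yes. The table runs for both injections and placebo comes first on the same day. Every man who completes Visit 2 as the table sets out has one post-saline and one post-morphine immersion.

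**Step 3: does the analysis use it?** Section 10a does not say so. The only opiate-versus-placebo changes described there are for binding potential and the subjective scales, and that sentence concerns correlations.

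**Step 4: what could omitting it do?** The plan has no figure for pain response to reproduce, and no SD or basal difference, so this is an illustration.

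Inputs: n = 40 per genotype and significance level 0.05 (Section 10). A two-sided test is assumed, since sidedness is not stated. Also assumed: normal values, equal variances, and the same shift from morphine in both genotypes. The basal difference d, in SDs of a single measurement, is assumed.

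The two-sample t test has df = 2 × 40 − 2 = 78 and noncentrality d × √(n/2) = d × √20 = 4.472d.

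| Assumed d | Noncentrality | P(significant), raw post-morphine values | P(significant), morphine minus placebo |
|---|---|---|---|
| 0.2 | 0.894 | 0.143 | 0.05 |
| 0.3 | 1.342 | 0.263 | 0.05 |
| 0.5 | 2.236 | 0.598 | 0.05 |

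The last column stays at 0.05 because a basal difference present in both immersions subtracts out.

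**Step 5: what does the change score cost in precision?** With equal variances and correlation r between a man's two immersions, the variance of the difference relative to a single value is 2 − 2r. This is 0.8 at r = 0.6 and 0.4 at r = 0.8 (r assumed). It exceeds 1 when r is below 0.5; at r = 0.3 it is 1.4. The difference detectable with 80% power is (1.960 + 0.842) × √(2/40) = 0.626 SD for a single value. Multiplying by √(2 − 2r) gives 0.741 SD at r = 0.3 and 0.396 SD at r = 0.8 for the change.

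**Step 6: the cut-off.** Immersion ends at 3 minutes. As an illustration, a man who lasts 2 minutes after saline can show at most 3 − 2 = 1 minute of gain; one who lasts 1 minute can show 3 − 1 = 2 minutes. If one genotype has longer basal endurance, the cap alone can shrink its change and produce a genotype difference. The 0.05 in Step 4 therefore assumes that few times reach the cap.

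**The case against.** The best defence has four parts.

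1. The sentence on baseline measures hands the timing to the flow-sheet, and the Table for Visit 2 is the only schedule for that visit. The text can thus be read as loose wording with the table in control. This stands in part: the text is ambiguous rather than a firm requirement. But the summary and the baseline step before placebo point the other way, and the footnote can be read either way.
2. A reader might infer that pain response has no reference at all. The documents do not support that: the post-placebo immersion is scheduled for every man.
3. Section 10a does not say that raw post-morphine pain times will be compared. In its wording, the post-morphine qualifier attaches to binding potential, and the laboratory responses are left undefined. This stands: the defect is an unspecified variable, not a declared wrong analysis.
4. A reader might also take Section 1 as showing that G-carrying men differ in cold pain. It concerns pressure pain, and its wording leaves unclear whether the threshold or the difference is the larger in men. It makes a basal difference plausible and gives no size for cold-water times.

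**Conclusion.** The point holds in a limited form. The summary, the Visit 2 text, the table and its footnote do not agree on a pre-injection cold pressor test and must be reconciled. Section 10a does not tie the pain outcome to the drug-free value that the study already collects.

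If raw post-morphine values were compared, the chance of a spurious genotype finding would be about 14%, 26% or 60% at basal differences of 0.2, 0.3 or 0.5 SD, against a nominal 5%. Those figures rest on assumed basal differences, equal analgesia and a two-sided t test with 40 per group. The documents establish neither a cold-pain difference nor that raw values will be used. It would go too far to say that the pain outcome cannot answer the study question: the data to answer it are scheduled.

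Pain response is a secondary measure, and neither primary outcome is affected. The change should be made because it is nearly free.

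**What to change.** - **Reconcile the schedule.** Bring the summary, the Visit 2 text, the table and the blood-draw footnote into agreement, so that every man has the same immersions at the same times. The analysis below needs only the two in the table.
- **Define the outcome in Sections 9b and 10a.** Use each man's post-morphine minus same-day post-placebo value, for pain threshold and for endurance. Compare that change by genotype.
- **Report post-placebo values by genotype** as the description of basal pain sensitivity.
- **Deal with the cut-off.** Treat endurance times at 3 minutes as censored, for example in a repeated-measures model whose genotype-by-condition term is the target. Otherwise, add a sensitivity analysis and report how many men reach the cap by genotype and condition.
- **Do not rely on the placebo value as a covariate alone.** In non-randomised groups with a basal difference d and the equal-variance assumption above, covariate adjustment removes rd and leaves (1 − r)d. That is 0.4d at r = 0.6 and 0.2d at r = 0.8.

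The cost is protocol and analysis wording; the analysis needs no extra immersion. One limit should be stated: placebo always comes first, so the average morphine effect includes an order effect. It cancels in the genotype contrast only if it is equal across genotypes. The change score also loses precision if the two immersions correlate below 0.5.

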Mesolimbic dopamine (DA) release is a key signal for drug reward, and endogenous opioids are thought to exert their effects in part by modulating the activity of this system. A functional μ -opioid receptor (OPRM1) A118G single nucleotide polymorphism (SNP) has been associated with increased risk for heroin addiction in some studies. This polymorphism has been shown to confer differential pain sensitivity and to alter the release of DA following an alcohol challenge. The objective of this study is to examine the role of the A118G OPRM1 polymorphism for responses to a challenge of an opiate (morphine) with regard to psycho-physiological variables measured in the laboratory and for brain dopamine release measured by [^{11}C]raclopride PET.

Study population

Healthy male participants who have had experience with oral prescription analgesics (e.g., Oxycontin, Vicodin, Percocet, oxycodone) will be recruited for the study. These volunteers will be screened to obtain samples of two groups of subjects: 1) persons homozygous for the major 118A allele (118AA genotype); 2) persons carrying one or two copies of the variant 118G allele (118AG or 118GG genotype, hereafter called 118GX). We will recruit up to 120 participants to obtain 40 completers per genotype for the study.

Design

We will compare the response of these groups to a challenge with morphine given intravenously. Participants will receive a standardized IV challenge of morphine (10.0 mg/70 kg over 1 minute; morphine concentration 2 mg/ml). Pre and post injection measures will be made in two areas: 1) subjective response as measured by standardized questionnaires, and 2) measures of physiological response, including pupil response to light, respiratory rate, oxygen saturation and a pain rating from putting a hand in cold water and blood chemistries. In addition, during this visit, participants will wear the AutoSense mobile physiological monitor; parameters measured by AutoSense include respiration rate, heart rate, heart-rate variability, skin conductance, and activity level. The injection will be repeated in all participants in the PET scanner, once with morphine and once with normal saline. Dopamine release will be assessed by determining the difference between the binding potential for [^{11}C]raclopride, a positron emitter labeled ligand which binds preferentially to D2 receptors during saline administration and its binding potential during morphine administration.

Outcome measures

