We hypothesize that 118GX subjects will have significantly different subjective response to the challenge than 118AA subjects as observed in participants receiving alcohol in a similar study (Ramchandani et al. 2011). However, the genotype effect on the response may be opposite from the effect of genotype on the alcohol response. We also hypothesize that the PET studies with [^{11}C]raclopride will show that 118GX subjects have less dopamine release during morphine administration than 118 AA subjects.

Table of Contents

1. Introduction/ Scientific Rationale	5
2. Study objectives or hypotheses	8
3. Subjects	9
4. Study Design and Methods	11
5. Storage of data and samples:.....	19
6. Additional Considerations	20
7. Risks/ discomforts.....	20
8. Subject monitoring.....	23
9. Outcome measures	23
10. Statistical Analysis.....	24
11. Human Subjects Protection.....	25
12. Anticipated Benefit	28
13. Summary/ classification of risk:	28
14. Consent documents and process	29
15. Data and Safety monitoring	29
16. Quality Assurance.....	30
17. Adverse event reporting	31
18. Alternatives to participation or alternative therapies	31
19. Confidentiality	31
20. Conflict of Interest	31
21. Technology Transfer	32
22. Research and Travel Compensation.....	32
23. References.....	33
Appendix I - Questionnaires	38
Appendix II. Recruiting advertisements	49
Appendix III. Screening questionnaires for Patient Recruitment Office	50
Appendix IV. Investigator's Brochure.....	53
Appendix VI. Other – Evaluation to sign consent and expected answers	54
Appendix VII. Results from mouse study.....	56
Appendix IX. 1SE Inpatient Nursing Information Sheet.....	57
Appendix X. Plan for clinical monitoring of participants receiving morphine at NIDA ..	59
Appendix XI. Plan for clinical monitoring of participants receiving morphine at the NIH Clinical Center in the Course of PET sessions	61

List of Abbreviations

ACTH - Adrenocorticotrophic hormone

aCPRS – abbreviated Comprehensive Psychopathology Rating Scales

BPI - Brief Pain Inventory

DA – dopamine

DEQ – Drug Effects Questionnaire

DTI – Diffusion Tensor Imaging

OPRM1 – gene for μ opiate receptor subtype 1

PSQI - Pittsburgh Sleep Quality Index

ROI – Region of Interest

VAS - visual analog scale

1. Introduction/ Scientific Rationale

Background

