
2. Study objectives or hypotheses

a. Hypotheses:

Homozygous carriers of the 118A allele of the μ -opioid receptor will show greater positive subjective response to the morphine than those carrying one or two copies of the

118G allele (118GX), paralleled by lower binding potential for [¹¹C] raclopride following morphine injection because of greater dopamine release than carriers of the G allele.

Objectives:

- a. Primary objectives:** To examine the role of the μ -opioid receptor polymorphism OPRM1 A118G on the subjective and objective effects, including dopamine release, of the μ -opioid agonist morphine.
- b. Secondary objectives:** A number of exploratory analyses will be carried out with the collected data to generate hypotheses on the relation of patient characteristics (e.g. family history of alcohol/drug use disorders, pain, mood, etc.), physiological opiate responses (e.g., pupil constriction, cardiovascular parameters such as respiratory rate and % oxygen saturation as measured by Pulse Ox), endocrine responses (cortisol, ACTH), pain threshold (measured by cold pressor test), MRI scans, and positive psychological effects (as measured via visual analog scale) with DA release measured by PET.

3. Subjects

a. Description of study populations

i. Brief description of subject groups

Subjects will be 21-55 year-old, non-nicotine dependent male volunteers who have taken prescription pain pills without negative effects in the past, but are not currently taking them or dependent on them. All participants will be in good health, non-smokers or light smokers (< 20 cigarettes/week), current non drinkers or social drinkers; participants should not meet DSM IV criteria for alcohol abuse or alcohol dependence. Subjects will be recruited into two groups: 1) subjects homozygous for the major 118A allele (118AA genotype) of the OPRM1 polymorphism; 2) subjects carrying one or two copies of the variant 118G allele (118AG or 118GG genotype, hereafter called 118GX) of the OPRM1 polymorphism.

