Post-placebo) and post-morphine injection measures will be made in two areas: 1) subjective response as measured by a standardized questionnaire (DEQ), and 2) objective measures response. We will determine their response to a cold pressor pain test, and a measurement of their pupillary constriction as well as several other tests of their response to the morphine, including continuous Pulse Ox monitoring and intermittent monitoring of their respiratory rate, heart rate, EKG and blood pressure. Blood will be collected to measure plasma ACTH and cortisol levels as they may be suppressed by activation of the μ -opioid receptor. Retrospectively, participants will be asked to evaluate their peak experience to the morphine on a Likert-like visual analog scale (VAS), which will include sedation, euphoria, dizziness, fatigue, depression, tremors, anxiousness, upset stomach/nausea, dry mouth, and headache, which are common side effects of opiate administration (Appendix I). We hypothesize that 118AA subjects will have significantly higher subjective response to the morphine challenge than 118GX subjects.

On two more separate visits, at least a week apart (Visits 3 and 4), participants will report to the Clinical Center in Bethesda for an overnight stay before each PET scan. We will repeat the injection procedure in all participants twice in the PET scanner, once injecting morphine and once injecting saline, and assess the binding potential of [¹¹C]raclopride, a positron emitter labeled ligand which binds preferentially to D2 dopamine receptors. The difference between the binding potential following the saline injection and that during the morphine injection will provide a measure of dopamine release. We hypothesize that 118AA subjects will have a lower binding potential with [¹¹C]raclopride from the morphine injection relative to placebo, indicating greater amounts of dopamine release than those subjects carrying one or two copies of the G allele.

b. Recruitment

This study employs an experiment of nature, i.e. genetic variability, as a basis for group assignment. To obtain the respective groups, this protocol will be conducted in the following phases:

1. Recruitment of potential participants through approved advertising media (see draft ad in Appendix II).
2. Thorough screening of selected participants according to 06-DA-N415 (“Screening Protocol for the Evaluation of Potential Research Subjects”).

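### The primary genotype test is specified on morphine-scan binding potential alone, but the plan defines dopamine release as the placebo-to-morphine change

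*Combined protocol and SAP*

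**What the plan says.** Section 10a (Analysis of data/study outcomes) gives the primary analysis in one sentence covering all dependent variables. For PET, "post-morphine injection raclopride binding potential) will be analyzed using analysis of variance, with genotype as the independent factor". The candidate covariates are drug and alcohol history, family history and ancestry: self-reports and "genetically derived ancestry scores will be evaluated as covariates in the analysis". Neither the placebo scan nor a scan-condition term appears. Section 9 names the PET outcome only as "binding potential in striatal areas of the brain", without saying which scan or whether a change is meant.

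Other sections define the quantity of interest as a contrast of two scans:

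- Summary, Design: "Dopamine release will be assessed by determining the difference between the binding potential for" raclopride under saline and under morphine.
- Section 4a: "The difference between the binding potential following the saline injection and that during the morphine injection will provide a measure of dopamine release".
- Section 4d, PET procedure: the placebo day is the baseline, and percent change from it is said to be proportional to release.
- Section 10a, PET paragraph: release is estimated from the baseline and morphine scans, taken in randomised order.

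The hypotheses mostly follow that definition. The summary expects that "118GX subjects have less dopamine release during morphine administration than 118 AA subjects". Section 4a expects lower binding in 118AA subjects "from the morphine injection relative to placebo, indicating greater amounts of dopamine release than those subjects carrying one or two copies" of the G allele. Section 2 is the exception: it predicts lower binding potential for "raclopride following morphine injection because of greater dopamine release than carriers of the G allele", which is worded on the morphine scan but explained by release.

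**The concern.** A person's morphine-scan binding potential is his baseline D2 availability less whatever the released dopamine displaces. Comparing genotypes on that scan alone tests the sum of a baseline difference and a release difference. The hypothesis concerns only the second.

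Randomisation would make the baseline part zero on average, but genotype is not randomised; section 4b calls group assignment an experiment of nature. That section's demographic balancing is only attempted, and the ancestry covariates remove only the part of a baseline gap that ancestry explains. An analyst who follows section 10a literally could therefore report a receptor-availability difference as a dopamine-release difference, or miss a real release difference that a baseline gap offsets. This is one of the two primary outcomes.

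**Working it through.** **The plan's own figure.** Two-group ANOVA, f = 0.65, alpha 0.05, N = 22: λ = N·f² = 22 × 0.4225 = 9.295, critical F(1, 20) = 4.351, power 0.826. This matches the Power Analysis table. The table does not name the variable. The sample-size text describes the source study's genotype finding as a change in binding potential, so f = 0.65 is probably on the change scale.

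**Inputs.** From the documents: 40 completers per genotype, alpha 0.05, and a 9.5% reduction in receptor availability, which is the sample-size text's ventral-striatum figure for remifentanil. Assumed, because the documents give no values: baseline genotype gap D in SD units, between-scan correlation r from 0.5 to 0.9, between-person CV of 10, 15 or 20% (simulation only), and SDs that are equal at the two scans, or that shrink in step with the mean when release is proportional.

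**Formula.** For a standardised difference d with 40 per group, λ = 80 × (d/2)² = 20d², referred to F(1, 78).

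**1. False rejection when genotypes do not differ in release.** On the morphine scan the gap passes straight through, so d = D whatever r is.

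| D | λ = 20D² | Morphine-scan test rejects |
|---|---|---|
| 0.10 | 0.20 | 7.3% |
| 0.25 | 1.25 | 19.7% |
| 0.50 | 5.00 | 59.8% |

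If release is proportional but the spread does not shrink with the mean, d = 0.905 × D. The last two rows become 17.0% and 51.5%.

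*Absolute change.* If release is additive, the gap cancels and the rate is 5%. If every subject loses a proportion p = 0.095, then d = pD/√(1 + (1−p)² − 2r(1−p)). For D = 0.5 and r = 0.9: 0.0475/√0.190 = 0.109, giving 7.7%.

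| D | r = 0.5 | 0.7 | 0.8 | 0.9 |
|---|---|---|---|---|
| 0.25 | 5.1% | 5.2% | 5.3% | 5.7% |
| 0.50 | 5.6% | 5.9% | 6.4% | 7.7% |

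*Simulation* (20,000 runs per cell):

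| Test | D = 0.25 | D = 0.5 |
|---|---|---|
| Morphine scan | 18.9–20.1% | 59.1–60.6% |
| Absolute change, additive release | 4.8–5.4% | 4.8–5.4% |
| Percent change, additive release | 4.8–5.9% | 5.2–7.4% |
| Percent change, proportional release | 4.8–5.3% | 4.8–5.3% |
| Absolute change, proportional release | 5.1–5.8% | 5.3–7.9% |
| ANCOVA on the placebo scan | 5.5–9.7% | 7.6–23.9% |

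ANCOVA keeps residual bias because it removes only r times the baseline gap.

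**2. Hiding a real difference.** Take a release difference that absolute change detects with 80% power: d = 0.634 on the change scale. On the morphine scan, in SD units of binding, this is δ = 0.634 × √(2(1−r)). An opposing baseline gap is subtracted from δ. Rejection in the correct direction:

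| r | δ | No gap | Gap 0.25 SD | Gap 0.5 SD |
|---|---|---|---|---|
| 0.5 | 0.634 | 80% | 40% | 9% |
| 0.7 | 0.491 | 58% | 19% | 2% |
| 0.8 | 0.401 | 43% | 10% | <1% |
| 0.9 | 0.284 | 24% | 4% | <1% |

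The no-gap column is ordinary loss of precision and depends on r. At r = 0.3 it reverses: the morphine-scan test has 91% power against 80% for change. Only the fall from that column to its right is due to the baseline gap.

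**The case against.** The strongest reply is that the section 10a wording is shorthand. It is one item in a parenthetical list, the PET paragraph that follows describes the two-scan comparison, and a placebo scan is acquired on every subject to serve as baseline. An analyst reading the whole plan might well test the change, and it is not established that the trial would be analysed on the morphine scan alone. But the PET paragraph only says how release is estimated. The one analysis the section names for the change is a correlation with baseline binding and subjective effects. No sentence makes the change the dependent variable of the genotype ANOVA, and the section 2 hypothesis is itself worded on post-morphine binding. Even the shorthand reading leaves absolute or percent change open for a primary outcome.

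The second reply is that the documents report no baseline D2 gap by genotype; the binding differences cited in section 1 are for a mu-opioid ligand. That is correct. The rates above are conditional on an assumed gap, and at 0.1 SD the inflation is small. The low power at r = 0.9 in step 2 is also mostly there before any gap is added.

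The uncertainty about f = 0.65 is a request for clarification, not part of the defect.

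**Conclusion.** The point holds and should be corrected before analysis. The primary-analysis sentence names a variable that is not the plan's own measure of dopamine release, and nothing else in the plan assigns the change score to the genotype test. That inconsistency needs no numerical assumption.

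Its consequence does. With 40 per group and no difference in release, the test as written rejects about 7%, 20% or 60% of the time at assumed baseline gaps of 0.1, 0.25 or 0.5 SD. For gaps of 0.25 and 0.5 SD, a change score stays between 5% and about 8% for r from 0.5 to 0.9. A gap in the opposite direction can hide a real release difference. The case rests on bias from a non-randomised baseline difference, not on a general gain in power, since the morphine-scan test is the stronger one when r is below 0.5 and there is no gap.

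**What to change.** In sections 2, 9 and 10a, state that the primary PET outcome is the placebo-to-morphine change in binding potential. Choose absolute or percent change in advance; percent change matches the PET procedure text in section 4d. Test genotype on that change, with the randomised scan order in the model. As sensitivity analyses, report the other change scale, and morphine-scan binding adjusted for placebo-scan binding, noting that the adjusted analysis stays biased if baseline binding differs by genotype. In the power section, say which variable f = 0.65 refers to.

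The cost is wording only, as both scans and their randomised order are already planned. Scan order uses one degree of freedom: with 77 instead of 78, 80.0% power becomes 79.99%. If r is below 0.5, the change score has less power than the morphine-scan test. If release follows the other scale, the chosen change score has a small bias: up to about 8% rejection in the ranges shown, and about 10% at r = 0.95 with a 0.5 SD gap.
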